14.4 Exclusion of Women, Minorities, and Children (Special Populations)

Racial and ethnic minorities will be included in the study at least proportional to their composition in the dentist's patient population. Individuals of any gender or racial/ethnic group may participate.

14.5 Participant Confidentiality

Participant confidentiality is strictly held in trust by the investigators, study staff, and the sponsor(s) and their agents.

The study protocol, documentation, data, and all other information generated will be held in strict confidence. No information concerning the study or the data will be released to any unauthorized third party without prior written approval of the sponsor.

Subjects will be assigned a unique identification number, which will be used to maintain study records and organize data transcripts. A file linking subjects' names with their unique identification number will be kept in a password-protected file on the CC's and RAS' computer.

The study monitor and other authorized representatives of the sponsor may inspect all study documents and records required to be maintained by the investigator, including but not limited to, dental records for the study participants. The clinical study site will permit access to such records.

14.6 Future Use of Stored Specimens and Other Identifiable Data

There will be no specimens collected for this study. There will be a barcode for the data collection form for each patient enrolled. Forms will be kept in a locked office at all times. They will be stored for three years from the conclusion of the study.

15 DATA HANDLING AND RECORD KEEPING

The investigators are responsible for ensuring the accuracy, completeness, legibility, and timeliness of the data reported. All source documents should be completed in a neat, legible manner to ensure accurate interpretation of data. The investigators will maintain adequate case histories of study participants, including accurate CRFs, and source documentation. The DMP is detailed in Appendix C.

Only study personnel (i.e., GPI, SPI, Co-I's, RCs, CC personnel) and clinical site monitors will have access to the study data elements in the study database as described in Section 15.3 Types of Data. Study personnel will include those who are on the approved IRB study protocol. All study personnel will have completed the required training elements for human subjects research certification.

15.1 Data Management Responsibilities

Data collection and accurate documentation are the responsibility of the study staff under the supervision of the investigator. All source documents must be reviewed by the study team and data entry staff, who will ensure that they are accurate and complete. Unanticipated problems must be reviewed by the investigator or designee.

Staff at the RAS will collect paper CRFs (pCRF) from practitioners and will enter data into the web system. For the pCRFs that are to be used as source documents (see Section 12), the RAS staff will ensure the forms are completed and the copies are maintained at practitioners' or regional sites. The RAS staff will ensure the data are entered and the discrepancies generated by the system are resolved in a timely fashion based on study requirements. The RAS staff will work with practitioners to clarify any data issues and maintain a tracking log for the data changes. To aid the data collection and data entry activities, the CC will provide pCRF completion and electronic data entry guidelines. Some or all of the pCRFs may also be sent to the CC for data entry by CC staff.

All data reported in the SMS will be checked by the CC staff for completeness and consistency. Any data issues identified will be communicated with the study team as appropriate according to the procedures specified in the DMP.

15.2 Data Capture Methods

Patient data will be collected via pCRFs. The post-study questionnaire, pre- and post-study vignettes will be completed electronically via the SMS. The practitioners will be given either a link to the questionnaire and vignettes and/or a unique code in order to complete the questionnaire and vignette.

Study-specific pCRFs will be developed to include fields for all data elements required for practitioner and patient assessments. A Web-based data collection system will ensure that all required data are collected in the study database. Data fields in the database will be programmed to allow only certain values and ranges so that data entered from the web system can be validated and data errors be corrected. Reports and tools will be developed to help monitor the visit and data activities. The reports with the summary of the data completion by participants will be made available on the network web site.

After the paper data collection has been completed for a participant, the study materials for the participant may be placed in the participant's research file. The participant log will be consulted

to obtain the name of the patient corresponding to the study ID number printed on the CRF so that the dentist can cross-check information on the study form with the patient's dental chart. Questions about the data will be resolved by conferring with the staff member(s) who completed the CRF.

For the online post study questionnaire and vignettes the SMS will ensure that all required data are collected per protocol requirements, and the data fields in the system are checked for completeness and consistency so that data entered into the web system can be validated and data errors be corrected. Edit checks will be programmed into the web survey to correct data issues in real time. Reports or tools will be developed to help monitor the data activities. The reports with the summary of the data completion by the participants will be made available on the network web site if requested.

15.3 Types of Data

Data that will be collected include responses from the pre- and post-study vignettes that will be completed by the practitioner. Responses from the patient data collection form will include demographic, lesion characteristics, and caries assessments.

15.4 Schedule and Content of Reports

Reports to monitor enrollment will be produced every two weeks during the participant enrollment period, until enrollment targets are attained and enrollment is closed. These reports will contain a section for accrual information in aggregate and will also contain separate sections for each region, with information regarding participant accrual by site.

Reports to the DSMB will be produced at least annually, and may be produced more frequently at the request of the DSMB. As noted in Section 9 Study Oversight, most data elements for inclusion in the DSMB reports will be clearly defined at the organizational meeting of the DSMB.

Study progress and interim analysis reports that address objectives will be produced at the discretion of the CC Statistician, in consultation with the SPI, and other study team members. The content of these reports will be determined by the CC Statistician, in consultation with the SPI, and other study team members.

The procedure for locking the database prior to final analysis will be detailed in Section N of the study DMP, in accordance with the CCs *SOP DSD-001: Development of a Data Management Plan* (see Appendix C) and *SOP DSD-405: Data Lock*. Briefly, the Oracle Clinical (OC) data will be locked and the final SAS datasets will be generated at the end of the study. Prior to locking the database, the Clinical Data Manager (CDM) or designee will ensure all data is complete and clean. Then, the CDM will obtain approval from the Project Manager to proceed with the data lock. The CDM will then direct the Database Development Manager to lock the database. The date and time of database lock will be documented. All team members will receive written notification from the CDM or designee when the database lock is complete.

No masking or coding is anticipated for this study.

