Randomization assignments will be performed by the CC via the National Dental PBRN practitioner database. The RAS staff will notify the practitioners on their randomization assignment. Randomization assignments will be stratified by region; therefore, each region will receive the devices prior to the start of the study. Once the RAS staff receives notification of the practitioner's randomization assignment, the practitioner will receive the device (if assigned to arm) from the RAS.

Following device familiarization if randomized to a device arm, practitioners will participate in the intervention period. We anticipate the intervention period to take approximately eight weeks per practitioner to train on the devices and enroll/complete 20 patients each with one lesion. Our previous study had shown that practitioners, on average, enrolled 19 patients per month. Each patient's (subject's) participation will be limited to the duration of the dental visit. The patient will undergo further caries detection using a device if in a device arm, and data collection and recording procedures will be performed. Practitioners randomized to the no device arm will begin the intervention stage after having received their randomization assignments.

Following the intervention phase, practitioners will complete a post-study vignette with scenarios and clinical photos. This will be completed online. For those assigned to a device arm, practitioners will also complete a post-study questionnaire on how they "self-trained" on the device, resources utilized for device familiarization, and utility of the device. For those not assigned to a device arm, practitioners will complete a post-study questionnaire on the vignette and participation in the study.

Pilot Testing

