11.3 Final Analysis Plan

This is the planned analysis based on the data we plan to collect. An appropriate statistical model must take into account both the level of measurement of the outcome variables and the study design. Both of the primary outcome variables, surgical treatment of the lesion and extension into dentin, may be appropriately represented as dichotomous variables. Each practitioner will be randomized to use a single device, or no device and no a priori study design levels defined within the level of practitioner. This approach yields a two-level hierarchical study design. A characteristic of this two-level model is the presence of correlation among the multiple observations obtained from each practitioner. The primary analysis framework will be based on mixed-model logistic regression analysis, implemented with generalized estimating equations (GEE), accounting for correlation among the clusters of observations made by the same practitioners. These models will include a term representing the individual practitioner as a random effect and study arm as a fixed effect. Additional control variables, including region, may be included if it is found that these are needed to account for possibly different distributions of practitioner or patient characteristics. Details of the analysis approach and related considerations are provided in Appendix E

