Appendix E: Statistical Analysis

The primary analysis framework will be based on mixed-model logistic regression analysis, implemented with generalized estimating equations (GEE) to account for correlation among the clusters of observations made by the same practitioners and to provide valid comparisons among the study groups.

Initial exploratory analyses will be conducted for the entire study data set, in order to characterize the empirical distributions of each variable, to identify possible errors in the data, and to evaluate the proportion of missing values. Since the data for Specific Aims 1 through 3 are collected at a single time point, patient-level missing values are anticipated to be unlikely, compared to concerns that arise in studies that include follow-up. If a patient rescinds consent during the study procedures, the practitioner can recruit a replacement patient, as this will not affect the randomized intervention assignment.

The analyses will include all observations that have valid values for the variables in each of the respective analyses. No attempt to replace or impute values that are missing is planned, as this would require assumptions related to the associations that are to be investigated, and could allow pre-analysis expectations to influence the study findings. If a substantial number of missing values is observed, the distribution of these will be evaluated in order to determine whether the missingness can be reasonably assumed to be at random. If this situation holds, then missing values would reduce power, but would not bias the estimates. If missing values are found to occur non-randomly, then the mechanism leading to missing values must be taken into account in the analysis model, for instance, by including variables that are found to be related to missingness. The proposed sample size anticipates that some values may not be obtained, and provides for adequate power despite having up to approximately 20% of observations having missing values for some variables, depending on the differences and level of ICC that are actually observed in the study.

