For evaluation of differences in proportions of lesions treated operatively among the intervention groups, the analysis data set will include all SOCLs that are enrolled by the study practitioners. The outcome variable for this analysis will be a dichotomous variable indicating whether the SOCL was treated operatively. Proportions of SOCL treated operatively will be calculated for each study arm. Confidence intervals, adjusted for correlation within clusters (practitioners), will be estimated from the GEE models. Statistical tests for differences in proportions among the three study arms will be based on Type III tests from the GEE analysis, controlling for the effect of clustering by practitioner. An indicator variable representing the study arm will be included as a fixed effect in this model, and a term representing the individual practitioners will be included as a random effect. The effect of regional site will be evaluated as a fixed effect, and will be included in the model if it explains a statistically significant portion of the observed variation in the outcome variable. The two pre-planned comparisons of the device versus no-device arms will be evaluated using contrasts, and will be tested using Chi-square tests of score statistics. Because these are pre-planned comparisons, each of these tests will be conducted at the 95% confidence level, using per-comparison error rates.

For the comparison of proportions of lesions treated operatively that have caries extending into dentin, the analysis data set will include all SOCLs that were treated operatively by the study practitioners. The outcome variable will be a dichotomous variable indicating whether the lesion extended into the dentin. The analysis will be identical to that utilized for Aim 1, except for the reduced analytic sample. GEE-based mixed-model logistic regression will be used to estimate confidence intervals for proportions of SOCLs extending into dentin, controlling for clustering by

practitioner and, if needed, for regional differences. Two pre-planned comparisons will be conducted using contrasts to compare each of the device study arms with the no-device arm.

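### No masking is anticipated while control variables, region and missing-data adjustments stay open until the data are seen, so the primary model could be chosen with results by arm in view

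*Protocol*

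**What the plan says.** **Masking and access.** Protocol Section 15.4 closes with "No masking or coding is anticipated for this study". Section 15 gives the access list for the database: "Only study personnel (i.e., GPI, SPI, Co-I's, RCs, CC personnel) and clinical site monitors will have access to the study data elements in the study". Section 15.4 also provides that "Study progress and interim analysis reports that address objectives will be produced at the discretion of the CC Statistician, in consultation with the SPI". Section 13 lets interim datasets go to the statistician before database lock.

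**Choices left to the data.**
- *Control variables.* Section 11.3: "Additional control variables, including region, may be included if it is found that these are needed to account for possibly different distributions"; the distributions meant are those of practitioner or patient characteristics. No list, threshold or time point is given.
- *Region.* Section 11.3 ties it to differing distributions of characteristics. Appendix E says instead that it "will be included in the model if it explains a statistically significant portion of the observed variation in the outcome variable", with no significance level. Section 4 says "Randomization assignments will be stratified by region".
- *Missing data.* Appendix E starts from complete cases without imputation. If a substantial number of values is missing and the pattern looks non-random, "then the mechanism leading to missing values must be taken into account in the analysis model"; the example given is to add variables linked to missingness. Neither trigger is defined.

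Section 11.3 and Appendix E also plan descriptive analyses linking practitioner and patient characteristics to the outcomes. Neither says that the primary model is fixed first.

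**The concern.** Dentists cannot be masked to having a device, but the people who settle the analysis model can be kept from seeing results by arm. The protocol does not anticipate this, and it leaves open choices that can move the primary estimates. When several models are defensible and the arm effect under each can be seen, a choice made in good faith can still drift towards the more striking result. The nominal 5% level then no longer describes the procedure, and a later reader has no record with which to exclude it. Appendix E tests each device-versus-control contrast at the 95% level with per-comparison error rates, so no multiplicity margin absorbs the excess.

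**Working it through.** **1. The plan's own figure.** The protocol gives no figure for this point. The nearest is the power of about 92% in Section 11.2 (50% vs 35%, ICC 0.05, 30 practitioners × 20 lesions per arm, Bonferroni-type level 0.05/2 = 0.025). It serves to check the inputs.
- Design effect: 1 + (20 − 1) × 0.05 = 1.95. Effective n: 600/1.95 = 307.7 per arm.
- Without continuity correction: z = (0.15 × √307.7 − 2.2414 × √(2 × 0.425 × 0.575)) / √(0.25 + 0.2275) = (2.631 − 1.567)/0.691 = 1.540, so power is 93.8%.
- With an approximate correction, n = 307.7 − 2/0.15 = 294.4: z = (2.574 − 1.567)/0.691 = 1.457, so power is 92.7%.

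The stated figure is reproduced to within two points. No stated number is wrong.

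**2. What each open choice leaves to judgement.**

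| Choice | Stated default or rule | What remains open |
|---|---|---|
| Control variables | None | Which variables, how need is judged, and when |
| Region | Two rules: differing distributions (11.3); significance against the outcome (Appendix E) | Which rule governs, and at what level |
| Missing data | Complete case, no imputation | What counts as substantial or non-random, and which variables are added |

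**3. How much selection could matter.** Simulation under no device effect, for one contrast on the first primary outcome:
- From the protocol: 30 vs 30 practitioners, 20 lesions each, six regions, ICC 0.05, two-sided 0.05 per contrast.
- Assumed: 0 to 6 optional practitioner covariates, each correlated 0.3 with the practitioner effect; ordinary regression on practitioner means in place of the planned GEE; an analyst who always takes the smallest p-value over every include/exclude combination.
- 4,000 replicates (1,500 for six covariates).

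| Optional terms | One fixed unadjusted model | Smallest p-value taken |
|---|---|---|
| Region only | 5.0% | 5.3% |
| Region + 2 covariates | 4.9% | 7.8% |
| Region + 4 covariates | 5.1% | 11.2% |
| Region + 6 covariates | 4.9% | 14.3% |

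The Monte Carlo standard error of the 11.2% entry is √(0.112 × 0.888/4000) ≈ 0.5 points.

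A second simulation (2,000 replicates, covariate–outcome correlation 0.15–0.25) gave 6.6% with one covariate, 7.2% with two, and 10.2–12.4% with four. The two sets of assumptions are comparable. The practitioner effect has variance 0.25 × 0.05 = 0.0125, and sampling adds (0.25 − 0.0125)/20 = 0.0119. A correlation of 0.3 with that effect is therefore 0.3 × √(0.0125/0.0244) ≈ 0.21 with the observed practitioner rate.

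**4. Would coding the arms A/B/C cure it?** No. A two-sided p-value does not change when the two labels in a contrast are swapped, and the three-arm Type III test does not change under any relabelling. The same search on coded arms returns the same p-values. The codes may also reveal themselves, since Section 11.2 expects 50% opened without a device and 30–35% with one. If the arm variable is withheld or scrambled, the chosen model cannot depend on the true arm contrast, and the test keeps the level of a fixed model.

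**The case against.** The strongest reply is that this is SAP territory. Covariate lists, missingness thresholds and sign-off dates commonly sit there, and a SAP not seen here may fix them all. That stands for the missing detail. It does not dispose of the point, because the protocol makes a positive statement about masking, gives two rules for region that do not match, and ties control variables to what is found in the data.

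Other points stand in part:
- Region has a stated criterion in Appendix E, and leaving region alone optional costs almost nothing (5.3%).
- Complete case is the default, chosen expressly so that prior expectations do not shape the findings, and patient-level missing values are thought unlikely. The main freedom is the open covariate clause, and its stated motive is balance of characteristics rather than the treatment result.
- The word coding is not defined. Participants already receive unique study codes, and the data management template in Appendix C uses the word for medical coding. Arm coding is the natural reading here but not the only one. The word masking carries the point either way.
- Database lock precedes the final analysis, and a second programmer or statistician verifies the analyses (Appendix B). Both help, but neither keeps results by arm from those choosing the model, and interim datasets can be issued before lock.

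A reader might infer that the protocol forbids masking, or that analysts will pick whatever favours a device. The documents support neither. The sentence says masking is not anticipated, the text shows opportunity and not conduct, and Section 2.2 frames the question in both directions.

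**Conclusion.** The point holds as a weakness in a stated design choice. The protocol anticipates no masking, leaves parts of the primary model to be decided from the data, and puts no barrier between those decisions and results by arm. The size is uncertain: per-contrast type I error of about 5% if only region is optional and roughly 7–12% with two to four optional covariates. These are worst-case selection figures, not predictions. They rest on an assumed number and strength of covariates, on practitioner-level regression instead of GEE, and on always taking the smallest p-value. They concern the first primary outcome; the second, with fewer lesions per practitioner, was not simulated. The change is worth making because it is cheap and the doubt cannot be removed afterwards. It is not a fatal flaw.

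**What to change.** Replace the masking sentence in Section 15.4 with a paragraph stating that:
- dentists are not masked;
- the control variables, region (included because it is the stratifier), missing-data handling and analysis sets are fixed, dated and signed off by the Coordinating Center statistician before any outcome result by arm is seen, working on data in which the arm variable and device-specific fields are withheld or randomly scrambled;
- true assignment is released for the primary analysis only after that sign-off and database lock;
- a separate unmasked programmer prepares any DSMB or interim report by arm.

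Bring the region wording in Section 11.3 and Appendix E into line with this. The cost is one paragraph, a small step for the data manager and a separate programmer role for by-arm reports before lock. Site procedures do not change.
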